4. INVESTIGATIONAL PLAN

4.1. Overall Study Design

This is an open-label monotherapy study of pemigatinib in subjects with myeloid/lymphoid neoplasms with FGFR1 rearrangement. Subjects will receive a QD dose of pemigatinib at 13.5 mg on a 2-week-on-therapy and 1-week-off-therapy schedule. With Protocol Amendment 3, the administration schedule was adjusted, and newly enrolled subjects will receive pemigatinib at 13.5 mg continuous administration (no planned dose hold). Subjects receiving treatment under previous versions of the Protocol may be switched to continuous administration after completing at least 3 cycles if there are no ongoing Grade 2 or higher related TEAEs. The written request to switch to continuous administration should be sent to the sponsor's medical monitor.

[figure not shown]
With Protocol Amendment 4, up-titration of pemigatinib was introduced. In any subject who has not had a serum phosphate level of > 5.5 mg/dL and who meet the criteria in Section [5.4.4](#), the investigator will increase the daily dose to 18 mg.

Full study drug administration information can be found in Section [5.2](#).

All potential subjects must have documentation of an 8p11 translocation known to activate FGFR1 through the site's own cytogenetics laboratory. Once documentation has been provided, the subject will then undergo screening to meet the rest of the inclusion/exclusion criteria. Once a subject has completed screening, the subject will be enrolled.

Treatment will start on Cycle 1 Day 1. Subjects will undergo regular safety assessments during treatment as well as regular efficacy assessments. Subjects will be allowed to continue administration in 21-day cycles until study treatment withdrawal criteria are met. The study design is shown in [Figure 4](#).

Figure 4: Study Design

^a Subjects with HSCT should continue to have peripheral blood smears, CBCs, differentials, bone marrow biopsies, bone marrow aspirates, and cytogenetics as per standard of care.

4.2. Measures Taken to Avoid Bias

This is an open-label study; no comparisons will be made between subjects or against historical controls. Measurements of safety and efficacy are objective measurements, and only comparisons to pretreatment conditions will be made.

4.3. Number of Subjects

4.3.1. Planned Number of Subjects

Approximately 46 subjects are planned for enrollment.

4.3.2. Replacement of Subjects

Not applicable.

4.4. Duration of Treatment and Subject Participation

After signing the ICF, screening assessments may be completed over a period of up to 28 days. Each subject enrolled in the study may continue to receive study treatment in continuous 21-day cycles. At the point when the subject discontinues study drug (pemigatinib), the treatment period will end, and the subject will enter the follow-up period (see Section 6.4). Study participation is expected to average approximately 6 months per individual subject.

4.5. Overall Study Duration

The study begins when the first subject signs the ICF. The end of the study is expected to occur when the last subject enrolled has completed 24 months of follow-up from their first postbaseline response assessment.

If there have been ≤ 2 subjects on study for more than 8 months, then a database lock of the study may occur to allow for the analysis of the study data. Any remaining subjects may continue to receive study treatment as per the Protocol. The remaining subjects are considered to be on study until a discontinuation criterion is met and written notification is provided to the sponsor.

4.6. Study Termination

The investigator retains the right to terminate study participation at any time, according to the terms specified in the study contract. The investigator/head of the study site (Japan) is to notify the institutional review board (IRB)/independent ethics committee (IEC) in writing of the study's completion or early termination, send a copy of the notification to the sponsor or sponsor's designee, and retain 1 copy for the site study regulatory file.

The sponsor may terminate the study electively, if required by regulatory decision, or upon advice of the study committee. If the study is terminated prematurely, then the sponsor will notify the investigators/head of the study site (Japan), the IRBs and IECs, and regulatory bodies of the decision and reason for termination of the study. For Japan, the decision from the sponsor will be via the head of the study site(s), who will notify the investigators and the IRBs of the decision and reason for termination of the study.

5. TREATMENT

See [Appendix F](#) for COVID-19-related guidance.

5.1. Treatment Assignment

5.1.1. Subject Numbering and Treatment Assignment

The interactive response technology (IRT) will be contacted at the beginning of screening to obtain a subject number. All subject numbers will be 6 digits; the first 3 digits will be the site number, and the last 3 digits will be the subject's number. This subject number will be maintained throughout the study and will not be reassigned. Subjects who withdraw consent or discontinue from the study after being assigned a subject number will retain their initial number.

Site staff will contact the IRT after screening is completed to enroll the subject and to allocate the subject to treatment assignment and obtain the initial study drug assignment. The investigator or designee will select the appropriate number of bottles of study drug from the stock that correspond to the dose provided by the IRT and dispense the study drug to the subject. All subsequent dispensing of study drug should follow this process. Refer to the IRT manual for detailed information.

If a subject is mistakenly given a bottle of study drug that is not the bottle assigned by the IRT, then the IRT help desk must be notified immediately. The reason for the misallocation of the study drug must be documented by the study site and reported to the IRB/IEC.

For subjects who signed an ICF but are not allocated and for subjects who are allocated but were not treated, refer to the electronic case report form (eCRF) Completion Guidelines for instruction on which eCRFs to complete.

5.1.2. Randomization and Blinding

Not applicable, as this is an open-label, single arm study.

5.2. Study Drug

5.2.1. Pemigatinib

5.2.1.1. Description and Administration

Pemigatinib will be self-administered as a QD oral treatment on a 21-day cycle. Subjects will take study drug for 2 weeks continuously (14 days) followed by a 1-week (7 days) break. The starting dose will be 13.5 mg. With Protocol Amendment 3, the administration schedule was adjusted, and newly enrolled subjects will receive pemigatinib at 13.5 mg continuous administration (no planned dose hold). Subjects receiving treatment under previous versions of the Protocol may be switched to continuous administration after completing at least 3 cycles if there are no ongoing Grade 2 or higher related TEAEs. The written request to switch to continuous administration should be sent to the sponsor's medical monitor.

Based on results from the food effect cohort in Study INCB 54828-101, pemigatinib may be administered with or without food.

5.2.1.2. Supply, Packaging, and Labeling

Study drug will be supplied as 2 mg and 4.5 mg tablets. All tablet excipients comply with the requirements of the applicable compendial monographs (Ph Eur, USP-NF; refer to the [IB](#)). Pemigatinib tablets will be packaged in high-density polyethylene bottles. No preparation is required.

All Incyte investigational product labels will be in the local language and will comply with the legal requirements of each country.

5.2.1.3. Storage

Bottles of tablets should be stored at room temperature, 15°C to 30°C (59°F to 86°F).

5.2.1.4. Instruction to Subjects for Handling Study Drug

The subject must be instructed in the handling of study drug as follows:

- To store the study drug at room temperature.
- To only remove from the study drug bottle the number of tablets needed at the time of administration.
- To not remove doses in advance of the next scheduled administration.
- To make every effort to take doses on schedule.
- To report any missed doses.
- To take study drug with a full glass of water.
- If the subject vomits after taking study drug, then the subject should not take another dose.
- To keep study drug in a safe place and out of reach of children.
- To bring all used and unused study drug kits to the site at each visit.
- If a dose of pemigatinib is missed by more than 4 hours, then that dose should be skipped, and the next scheduled dose should be administered at the usual time.

5.3. Treatment Compliance

Compliance with all study-related treatments should be emphasized to the subject by the site personnel, and appropriate steps should be taken to optimize compliance during the study. Compliance with pemigatinib will be calculated by the sponsor based on the drug accountability documented by the site staff and monitored by the sponsor/designee (tablet counts). Subjects will be instructed to bring the study drug with them to the study visits in order for site personnel to conduct tablet counts to assess study drug accountability. The drug accountability documentation will be used by the sponsor to calculate treatment compliance.

5.4. Treatment Interruptions and Adjustments

5.4.1. Dose Modifications

Dose interruptions and modifications may occur for individual study subjects. The occurrence of toxicities (related or unrelated to study drug) will guide decisions for treatment interruptions and discontinuation for individual subjects.

5.4.2. Criteria and Procedures for Dose Interruptions and Adjustments of Study Drug

Safety concerns should be discussed with the sponsor immediately upon occurrence or awareness to determine whether the subject should continue or discontinue study treatment. For subjects who present with possible or confirmed serous retinal detachment/retinal pigmented epithelium detachment (SRD/RPED) based on optical coherence tomography (OCT), the guidelines in [Table 2](#) should be followed. It is recommended to discuss the findings with the Incyte medical monitor before making changes to the subject's treatment.

Per CTCAE v 4.03, there is a grading for retinal detachment, however, this refers to rhegmatogenous retinal detachment (when a hole occurs in the retina) or exudative detachment (fluid accumulation due to inflammatory diseases). There is no exact CTCAE grading term for SRD/RPED secondary to FGFR inhibition (there is no hole in the macula, just fluid accumulation or detachment of retinal pigmented epithelium). Therefore, grading should be based on the CTCAE term "retinopathy."

Treatment with pemigatinib may be delayed up to 14 days to allow for resolution of toxicity. Subjects may resume treatment if no medical condition or other circumstance exists that, in the opinion of the investigator, would make the subject unsuitable for further participation in the study. The treating investigator should contact the sponsor to discuss the case of any subject whose treatment has been delayed for more than 14 days before restarting treatment with pemigatinib.

Table 2: Guidelines for Interruption and Restarting of Study Drug

Toxicity/CTCAE Grade	Action Taken	
Chemistry		

 AST and/or ALT is $> 5.0 \times \text{ULN}$. ALP $> 5 \times \text{ULN}$. 
Note: In subjects with bone metastasis-related elevations at baseline, contact sponsor to discuss clinical management and possible dose reductions.
	
Step 1: Interrupt study drug up to 2 weeks (14 days) until the toxicity has resolved to \leq Grade 1 except by approval of the medical monitor.
 
Step 2: If assessed as related to study drug, restart study drug at next lower dose; monitor as clinically indicated.
	
Hy's law: ALT $> 3.0 \times \text{ULN}$, ALP $< 2 \times \text{ULN}$, and bilirubin $\geq 2.0 \times \text{ULN}$; no evidence of biliary obstruction or other causes that can reasonably explain the concurrent elevation.	Discontinue treatment.	
Hematology		
ANC in subjects with baseline ANC $> 1.0 \times 10^9/\text{L}$	
ANC ($< 0.5 \times 10^9/\text{L}$)
 
ANC $< 1.0 \times 10^9/\text{L}$ with an oral temperature of at least 38.5°C OR with \geq Grade 3 infection
	
Step 1: Interrupt study drug up to 2 weeks (14 days) until resolved to \leq Grade 1 or to baseline.
 
Step 2: If assessed as related to study drug, restart study drug at next lower dose; monitor as clinically indicated.

Platelets in a subject with baseline platelets $> 75 \times 10^9/\text{L}$	
Platelet count $< 25 \times 10^9/\text{L}$
 
Platelet count $25-50 \times 10^9/\text{L}$ and sustained (> 7 days) or associated with bleeding
	
ANC in subjects with baseline ANC $< 1.0 \times 10^9/\text{L}$	$\geq 50\%$ decrease from baseline ANC and not thought to be due to disease progression or concomitant medications per treating physician	
Step 1: Evaluate underlying disease based on peripheral blood and bone marrow assessment as needed.
 
Step 2: Consider dose interruption if cytopenias are NOT due to underlying disease.
 
Step 3: Restart study drug at next lower dose; monitor as clinically indicated.

Platelets subjects with baseline platelet count $< 75 \times 10^9/\text{L}$ only	$\geq 50\%$ sustained decrease (> 7 days) from baseline platelet count and not thought to be due to disease progression or concomitant medications per treating physician	
Other toxicities, including SRD/RPED		
Any Grade 1 or Grade 2 toxicity	Continue study drug treatment and treat the toxicity; monitor as clinically indicated. For increased serum phosphate, see Section 5.4.3 for the recommended approach for HP management. Subjects who have abnormal serum phosphate or calcium levels should have their levels monitored at least twice a week.	
Any Grade 3 toxicity, if clinically significant and not manageable by supportive care	
Step 1: Interrupt study drug up to 2 weeks (14 days), until toxicity resolves to \leq Grade 1 or to pretherapy baseline.
 
Step 2: If assessed as related to study drug, restart study drug at next lower dose; monitor as clinically indicated.
	
Any recurrent Grade 3 toxicity after 2 dose reductions	Discontinue study drug treatment and follow-up per Protocol.	
Any other Grade 4 toxicity	Discontinue study drug treatment and follow-up per Protocol.	

ALP = alkaline phosphatase; ANC = absolute neutrophil count.

The sponsor recommends a maximum of 2 dose level reductions: subjects administered 13.5 mg can decrease to 9 mg, and if additional dose reduction is required, subjects can decrease to 4.5 mg. Subjects enrolled before Protocol Amendment 5 may have been reduced from 9 mg to 6 mg. The frequency of dosing (either intermittent or continuous) remains the same.

Subjects who are up-titrated to 18 mg from 13.5 mg can be reduced back down to a dose of 13.5 mg, followed by 9 mg and 4.5 mg reductions as needed.

With Protocol Amendment 5, a dose below 4.5 mg is not allowed. Subjects who were allowed doses below 4.5 mg previously should be given the option to increase their dose to 4.5 mg but may resume their lower dose if 4.5 mg cannot be tolerated.

5.4.3. Management of Hyperphosphatemia

Hyperphosphatemia is an expected on-target pharmacologic effect of FGFR inhibition. Hyperphosphatemia should be managed with diet modifications, phosphate binders and diuretics, or a dose reduction per the recommendations in [Table 3](#).

For Japan, the phosphate binder lanthanum carbonate hydrate is recommended for the treatment of hyperphosphatemia and will be provided by the sponsor.

Table 3: Recommended Approach for Hyperphosphatemia Management

Serum Phosphate Level	Supportive Care	Guidance for Interruption/Discontinuation of Pemigatinib	Guidance for Restarting Pemigatinib
> 5.5 mg/dL and ≤ 7 mg/dL	Initiate a low-phosphate diet.	No action.	Not applicable.
> 7 mg/dL and ≤ 10 mg/dL	Initiate/continue a low-phosphate diet and initiate phosphate-binding therapy once serum phosphate level is > 7 mg/dL. Monitor serum phosphate at least twice a week and adjust the dose of binders as needed; continue to monitor serum phosphate at least twice a week until return to normal range.	If serum phosphate level continues to be > 7 mg/dL and ≤ 10 mg/dL with concomitant phosphate-binding therapy for 2 weeks, or if there is recurrence of serum phosphate level in this range, interrupt pemigatinib for up to 2 weeks (not including the planned dose hold per treatment cycle).	Restart at the same dose when serum phosphate is < 7 mg/dL. If serum phosphate level recurs at > 7 mg/dL, restart study drug with dose reduction.
> 10 mg/dL	Continue to maintain a low-phosphate diet, adjust phosphate-binding therapy, and start/continue phosphaturic agent. Continue to monitor serum phosphate at least twice a week until return to normal range.	If serum phosphate level is > 10 mg/dL for 1 week following phosphate-binding therapy and low phosphate diet, interrupt study drug. If there is recurrence of serum phosphate level in this range following 2 dose reductions, permanently discontinue pemigatinib.	Restart study drug at reduced dose with phosphate binders when serum phosphate is < 7 mg/dL.

5.4.4. Up-Titration

Any subject treated at 13.5 mg QD will be titrated up to 18 mg QD using their current dose regimen with approval from the medical monitor if the subject meets the following criteria:

- Has been on study drug for at least 1 cycle.
- Has been compliant with taking study drug.
- Has no ongoing Grade 2 or higher treatment-related AE.
- Has not had hyperphosphatemia, defined as a serum phosphate level of > 5.5 mg/dL.

Subjects who are titrated up to 18 mg QD will begin the next cycle at the new dose level and must agree to all Cycle 1 assessments (PK and safety assessments [hematology and blood chemistry]). Up-titration may occur no earlier than Cycle 2 Day 1, so that subjects are observed for phosphate level and AEs for at least 1 cycle.

5.4.5. Criteria for Permanent Discontinuation of Study Drug

The occurrence of unacceptable toxicity not caused by the underlying malignancy will be presumed to be related to study drug treatment and will require that the study drug be permanently discontinued. Unacceptable toxicity is defined as follows:

- Occurrence of an AE that is related to treatment with the study drug that, in the judgment of the investigator or the sponsor's medical monitor, compromises the subject's ability to continue study-specific procedures or is considered to not be in the subject's best interest.
- An AE requiring more than 2 dose reductions. Note: Reducing down to original dose following up-titration does not count toward the number of allowed dose reductions.
- Persistent AE requiring a delay of therapy for more than 21 days unless a greater delay has been approved by the sponsor.

5.5. Withdrawal of Subjects From Study Treatment

5.5.1. Withdrawal Criteria

Subjects **must** be withdrawn from study treatment for the following reasons:

- The subject becomes pregnant.
- Consent is withdrawn. Note: Consent withdrawn means that the subject can no longer be followed. Subjects may choose to discontinue study treatment and remain in the study to be followed for progression and survival.
- Further participation would be injurious to the subject's health or well-being, in the investigator's medical judgment.
- The study is terminated by the sponsor.
- The study is terminated by the local health authority, IRB, or IEC.
- Unacceptable toxicity has occurred.

- Disease progression has been reported.
- Other antineoplastic treatment is initiated.

A subject **may** be discontinued from study treatment as follows:

- If, during the course of the study, a subject is found not to have met eligibility criteria, then the medical monitor, in collaboration with the investigator, will determine whether the subject should be withdrawn from the study.
- If a subject is noncompliant with study procedures or study drug administration in the investigator's opinion, then the sponsor should be consulted for instruction on handling the subject.

5.5.2. Withdrawal Procedures

In the event that the decision is made to permanently discontinue the study drug, the subject will be withdrawn from the study, and the EOT visit should be conducted. Reasonable efforts should be made to have the subject return for a follow-up visit. These visits are described in Section 6. The last date of the last dose of study drug and the reason for subject withdrawal will be recorded in the eCRF.

If the subject discontinues study treatment and actively withdraws consent for collection of follow-up data (safety follow-up or disease assessment), then no additional data collection should occur; however, subjects will have the option of withdrawing consent for study treatment but continuing in the follow-up period of the study for safety/efficacy assessments.

5.6. Concomitant Medications

5.6.1. Restricted Medications

Pemigatinib is predominantly metabolized by CYP3A4. There is a sufficient safety margin, with doses greater than the recommended Phase 2 dose of 13.5 mg QD having been tested, and up to 20 mg QD is tolerable (refer to the [IB](#)). The expected 50% increase in exposure in subjects who concomitantly use CYP3A4 moderate inhibitors is covered by the safety margin. Therefore, the use of moderate CYP3A4 inhibitors should involve careful monitoring, especially in relation to safety, while moderate CYP3A4 inducers and potent CYP3A4 inhibitors and inducers are prohibited (see [Appendix C](#)).

Careful monitoring is required when pemigatinib is concomitantly administered with OCT2 substrates such as dofetilide and metformin.

Calcium-based phosphate binding medications should not be used due to a concern for soft tissue mineralization.

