1.2. Study Rationale

Cancer has several common characteristics that can be observed across numerous tumor types. One common characteristic is the uncontrolled growth and survival of cells and their ability to become invasive throughout the body. Fibroblast growth factor signaling produces mitogenic, anti-apoptotic, and angiogenic responses in cells, which leads to a deregulated state. Evidence from several *in vitro* and *in vivo* tumor models has established the FGFs and FGFRs as oncogenes, and their expression has been found in numerous solid tumors or hematological malignancies. Several genetic alterations have been shown to generate overexpression of the FGF receptor, produce a receptor that is constitutively active, or lead it to a state where there is reduced dependence on ligand binding for activation ([Knights and Cook 2010](#)).

Tyrosine kinases are an especially important target in cancer therapy as they have a key role in growth factor signaling. Several tyrosine kinase inhibitors have been shown to be effective antitumor agents and have been approved in multiple oncology indications ([Arora and Scholar 2005](#)). Pemigatinib is a potent inhibitor of the kinase activity of FGFR1, FGFR2, and FGFR3 and has been shown to inhibit growth in several tumor models.

In the Phase 1 study (INCB 54828-101), several subjects were treated at dose levels ranging from 1 to 20 mg once daily (QD) for 2 weeks followed by 1 week off as well as continuous administration (no planned dose hold) in 21-day cycles. The maximum tolerated dose was not established. One subject with MPN FGFR1 8p11, treated with pemigatinib at 9 mg, 2 weeks on/1 week off, experienced a complete cytogenetic and morphological response with hematological improvement.

The Phase 2 starting dose has been established at 13.5 mg QD following the 2-weeks-on/1-week-off regimen. This dose was recommended based on safety, pharmacokinetics (PK), and preliminary signals of clinical benefit. With Protocol Amendment 3, a continuous administration regimen was introduced with a starting dose of 13.5 mg. This dose and regimen is considered

tolerable based on PK and safety data from study INCB 54828-101 ([Subbiah et al 2022](#)). The safety data for both the intermittent and continuous regimens are outlined in Section [1.3.2](#).

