1.3.2.1. Pharmacokinetic/Pharmacodynamic Summary

In Study INCB 54828-101, pemigatinib exhibited linear PK over the dose range (1 to 20 mg) evaluated. Pemigatinib is rapidly absorbed, attaining peak plasma concentrations in approximately 1 to 2 hours after oral administration, and the mean $t_{1/2}$ is 18.8 hours. At the 13.5 mg QD dose, the average steady-state C_{max} value is 256 nM, and the average AUC value is 2980 nM·h; mean steady-state oral clearance of pemigatinib is low (12.5 L/h), and apparent steady-state volume of distribution is moderate (293 L). The PK parameters for continuous administration are similar to those for intermittent dosing.

The projected average inhibition of FGFR2 based on PK and in vitro potency of pemigatinib ranged from 41% at 1 mg to 97% at 20 mg. Consistent with this projection, the observed inhibition of pFGFR2 in KATOIII cells spiked to ex vivo whole blood samples collected from subjects at trough was 82% after the 13.5 mg QD dose and 64% after the 9 mg QD dose. The steady-state plasma concentrations of pemigatinib after 13.5 mg QD dose that exceeded in vivo IC_{50} over a 24-hour dosing period is showed in [Figure 1](#). The magnitude and frequency of HP was also dose-dependent. In the 9 mg cohort, 1 of 3 subjects developed HP in Part 1; 3 additional subjects were enrolled at 9 mg in Part 2. Of a total of 6 subjects administered 9 mg, 4 experienced HP; in the 13.5 mg cohort, all 6 subjects developed HP, which was managed with

a low-phosphate diet and introduction of phosphate binders. Furthermore, the increase in serum phosphorus observed after treatment with pemigatinib was exposure-dependent (see [Figure 2](#)).

Figure 1: Pemigatinib Plasma Concentrations (Mean \pm SE) at Steady State After 13.5 mg QD Oral Doses of Pemigatinib

[figure not shown]
[figure not shown]

Figure 2: Serum Phosphate Versus Exposure

[figure not shown]
Therefore, based on a manageable safety profile and a favorable PK/PD profile, the targeted starting dose for Phase 2 is 13.5 mg. This dose is being tested in 2 additional Phase 2 protocols in subjects with urothelial cancer (INCB 54828-201) and cholangiocarcinoma (INCB 54828-202) previously submitted to IND 124,358 with the Division of Oncology Products 1.

In addition, PK data generated in the INCB 54828-101 study with continuous administration (9 mg and 13.5 mg) has shown concordance with the PK profile of subjects receiving interval administration for Cycle 1.

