Hyperphosphatemia is an expected on-target pharmacological effect of FGFR inhibition. The incidence of hyperphosphatemia, defined as any postbaseline phosphate level exceeding 5.5 mg/dL, has been observed in the majority of subjects treated with pemigatinib (refer to the [IB](#)

for complete data). Some subjects do not achieve hyperphosphatemia, and it is estimated that the pharmacological concentration of pemigatinib in these subjects is lower (see [Figure 3](#)).

Figure 3: Comparison of Steady-State Exposures for Pemigatinib 13.5 mg QD Between Subjects With Nonhyperphosphatemia and Hyperphosphatemia

AUC_{ss} = area under the curve at steady state; $C_{min,ss}$ = minimum blood plasma concentration at steady state; HP = hyperphosphatemia.

The increase in serum phosphorus observed after treatment with pemigatinib was exposure-dependent and followed a sigmoid relationship. A population E_{max} model of pemigatinib AUC and maximal serum phosphate change from baseline was developed. For those subjects treated with pemigatinib 13.5 mg who did not develop hyperphosphatemia, AUC for pemigatinib 18 mg was estimated using a linear exposure relationship. Maximal serum phosphate change from baseline for each individual was then estimated using a population model. The maximal serum phosphate after treatment with pemigatinib 18 mg was calculated by adding the baseline of serum phosphate. The simulation suggested that the serum phosphate would increase above 5.5 mg/dL after treatment with pemigatinib 18 mg for the subjects treated with pemigatinib 13.5 mg who did not develop hyperphosphatemia.

Therefore, Protocol Amendment 4 allowed up-titration of pemigatinib to increase the dose of pemigatinib in subjects who do not achieve hyperphosphatemia when treated with 13.5 mg QD. The goal is to increase the serum concentration of pemigatinib for subjects who are assumed to have lower exposure based on a lower serum phosphate level while on treatment. See [Section 5.4.4](#) for details.

Subjects will be monitored on an ongoing basis throughout this study as per the schedule of assessments (see [Table 4](#) and [Table 5](#)).

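### Protocol 5.6.1 says a 50% exposure increase from moderate CYP3A4 inhibitors is covered, but the data it cites do not support this at the 18 mg up-titrated dose

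*Protocol*

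**What the plan says.** Protocol 5.6.1 (Restricted Medications) notes that pemigatinib is mainly cleared through CYP3A4 and asserts a safety margin. The support it gives, with a reference to the Investigator's Brochure, is this: "doses greater than the recommended Phase 2 dose of 13.5 mg QD having been tested, and up to 20 mg QD is tolerable". It then concludes: "The expected 50% increase in exposure in subjects who concomitantly use CYP3A4 moderate inhibitors is covered by the safety margin". On that basis moderate inhibitors may be used with careful monitoring, while potent inhibitors and moderate or potent inducers are prohibited. The only study dose named in the section is 13.5 mg, and the permission is not limited by dose.

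Protocol 5.4.4 (Up-Titration) states: "Any subject treated at 13.5 mg QD will be titrated up to 18 mg QD using their current dose regimen". This needs medical monitor approval and four criteria: at least one cycle on drug, compliance, no ongoing related adverse event of Grade 2 or higher, and the phosphate criterion, "Has not had hyperphosphatemia, defined as a serum phosphate level of > 5.5 mg/dL". None of the four mentions CYP3A4 inhibitors. The Synopsis, Protocol 4.1 and SAP Section 3 repeat the step to 18 mg.

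Protocol 1.3.2.1 gives the dose-exposure relationship: "pemigatinib exhibited linear PK over the dose range (1 to 20 mg) evaluated".

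**The concern.** The coverage statement compares two quantities: exposure with an inhibitor, and exposure at the highest dose called tolerable. The comparison depends on the starting dose. From 13.5 mg there is room for an increase of about 48% before the 20 mg level is reached. From 18 mg there is room for about 11%. A statement argued from the first dose is worded so that a site would also apply it to the second.

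What is at stake is a safety premise. A site that follows the text as written may combine 18 mg with a moderate inhibitor in the belief that the Protocol has shown the resulting exposure to lie within tested experience. The documents describe no dose above 20 mg. The combination is not far-fetched: the moderate inhibitors in Appendix C include antifungals, antibiotics, antiemetics and calcium channel blockers.

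**Working it through.** **Inputs**
- Expected increase with a moderate inhibitor: 50%, a factor of 1.5 (Protocol 5.6.1).
- Highest dose called tolerable: 20 mg once daily (Protocol 5.6.1).
- Study doses: 13.5 mg at the start, 18 mg after up-titration (Protocol 5.4.4).
- Linear pharmacokinetics from 1 to 20 mg (Protocol 1.3.2.1), so exposures can be expressed as dose-equivalents.
- Mean steady-state exposure at 13.5 mg: "the average AUC value is 2980 nM·h" (Protocol 1.3.2.1).

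**Formulas**
- Dose-equivalent = dose × (1 + increase), compared with 20 mg.
- AUC = (2980 / 13.5) × dose-equivalent. For 20 mg this gives 2980 / 13.5 × 20 ≈ 4415 nM·h.

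**Step 1: the Protocol's own case, 13.5 mg**
- 13.5 × 1.5 = 20.25 mg-equivalent; 20.25 / 20 = 1.0125; AUC ≈ 4470 nM·h.
- The statement is reproduced to within 1.25%, with nothing to spare.

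**Step 2: the up-titrated dose at average exposure**
- 18 × 1.5 = 27 mg-equivalent; 27 / 20 = 1.35; AUC ≈ 5960 nM·h, twice the 13.5 mg mean.
- Linearity is stated only up to 20 mg, so 27 is an extrapolation.

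**Step 3: room before 20 mg is reached**
- From 13.5 mg: 20 / 13.5 − 1 = 48.1%.
- From 18 mg: 20 / 18 − 1 = 11.1%.

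**Step 4: sensitivity to the size of the interaction at 18 mg**
- +25%: 18 × 1.25 = 22.5 mg-equivalent (1.13 times 20 mg).
- +75%: 18 × 1.75 = 31.5 mg-equivalent (1.58 times 20 mg).
- Even half the expected increase goes past 20 mg at average exposure.

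**Step 5: sensitivity to lower exposure in up-titrated subjects**

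The aim of up-titration is stated in Protocol 1.3.2.1: "The goal is to increase the serum concentration of pemigatinib for subjects who are assumed to have lower exposure". Figure 3, which compares exposures by phosphate status, is not visible in the copy reviewed, so relative exposure r (dose-normalised, average = 1) is an assumption here. The equivalent is 27 × r, and the break-even value is r = 20 / 27 = 0.74.

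| Assumed r | 18 mg plus inhibitor, mg-equivalent | Within 20 mg? |
|---|---|---|
| 0.6 | 16.2 | yes |
| 0.74 | 20.0 | at the limit |
| 0.9 | 24.3 | no |
| 1.0 | 27.0 | no |

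Whether the statement holds at 18 mg therefore turns on a quantity that the text does not give.

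**The case against.** The strongest reply is that 5.6.1 anchors its margin to 13.5 mg and never names 18 mg, so this is a gap in scope and nothing is contradicted. It is true that the section makes no explicit claim for 18 mg. But the conclusion and the permission that follows carry no dose limit, in a Protocol that directs eligible subjects to 18 mg.

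Second, up-titrated subjects are selected for presumed low exposure, so 27 mg-equivalent may overstate what they reach. This stands as a limit on the size, and Step 5 gives the range. It does not rescue the statement: selection is by phosphate, not by measured exposure, and 5.6.1 does not use the argument.

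Third, in a subject already taking an inhibitor, the phosphate criterion acts on exposure that already includes it, and up-titration adds only 18 / 13.5 − 1 = 33%. That narrows the problem. It leaves open an inhibitor started after up-titration, on which 5.4.4 is silent.

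Fourth, there are controls: medical monitor approval, repeat Cycle 1 PK and safety assessments after up-titration, careful monitoring with inhibitors, and provision for reducing from 18 mg. These lower the risk but do not make the coverage statement true at 18 mg. The Investigator's Brochure may hold supporting data; it was not available, and if it does, the sponsor need only cite them. The animal margin in Protocol 1.3.1 does not clearly fill the gap: its claimed 20- to 25-fold margin is not what its own unbound AUCs give (0.125 / 0.06 = 2.1 and 0.148 / 0.06 = 2.5).

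Fifth, few subjects are affected. Protocol 1.3.2 reports a hyperphosphatemia event in 35 of 47 participants, leaving 47 − 35 = 12 without one. That is only a rough guide to how many could be up-titrated, because eligibility uses a laboratory threshold and other criteria; those also taking a moderate inhibitor would be fewer.

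A reader might also infer that 5.6.1 is text left over from before up-titration existed. The documents do not support that: the Amendment 4 summary in Appendix G lists up-titration and a revision of 5.6.1 in the same amendment.

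**Conclusion.** The concern holds for 18 mg. The data cited in 5.6.1 support the coverage statement at 13.5 mg and do not support it at the up-titrated dose. At average exposure the shortfall is 27 against 20 mg-equivalent, or 35%. Under assumed relative exposures of 0.6 to 1.0 the range is 16.2 to 27.0 mg-equivalent, with coverage only at about 0.74 or below. These figures rest on the Protocol's 50% increase, on linear pharmacokinetics extended past 20 mg, and on means; between-subject spread is not used.

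Two stronger readings should be resisted. One is that the statement already fails at 13.5 mg because 20.25 exceeds 20. A 1.25% difference against a rounded expected increase is not a defect. The other is that 27 mg-equivalent is unsafe. Protocol 1.2 says of the Phase 1 study: "The maximum tolerated dose was not established". So 20 mg is the top of the cited experience and not a demonstrated ceiling; the exposure is unsupported by the stated margin, which is a different thing from being shown to be harmful.

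No endpoint or efficacy analysis is affected. The point is still worth correcting, because a stated safety premise does not extend to a dose the Protocol itself uses.

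**What to change.** Reconcile Protocol 5.6.1 with 5.4.4, 4.1 and the Synopsis. Either limit the coverage statement to the dose levels that the cited data support, or cite the exposure data that extend it to 18 mg. If lower exposure in up-titrated subjects is the intended reason, 5.6.1 should say so and give the size of the difference. Which course is right clinically is for the sponsor; no dose or clinical rule is proposed here.

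Optionally, add to the SAP one cross-listing of moderate CYP3A4 inhibitor use during 18 mg treatment, with the treatment-emergent adverse events. SAP Appendix C already plans separate listings of concomitant medication (2.4.8), study drug administration (2.5.2) and adverse events (2.7.1), while in the visible text of SAP 6.6 phosphate binders are the only concomitant class singled out.

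The cost is a short Protocol text change and, if wanted, one listing built from data already collected.
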